3.8.2.1. Primary Analysis

The null hypothesis is that there is no difference in percent change from baseline in body weight at Week 12 between ALKS 3831 and olanzapine. The alternative hypothesis is that there is a difference between ALKS 3831 and olanzapine.

The primary endpoint will be analyzed by analysis of covariance (ANCOVA) with the multiple imputation (MI) method for handling of missing values. The model will include the treatment group and randomization strata (diagnosis [schizophrenia/schizopreniform disorder vs bipolar I disorder], region [US vs non-US] and baseline BMI [<25 vs ≥ 25 kg/m²]) as factors, and the baseline weight as the covariate. Only the on-treatment measurements will be included in the analysis. The following steps will be performed:

1. The missing data on body weight will be imputed using MI. If there is any subject whose missing data pattern is non-monotonic (defined as having missing data in between visits), the Markov Chain Monte Carlo (MCMC) method will be used to impute the data to a monotonic missing pattern (i.e., if the data is missing at the current visit, the data at all following visits are missing). A single Markov chain will be used with 200 burn-in iterations, 100 iterations between imputations and a Jeffrey's prior. Next, the missing data will be imputed sequentially by each visit using a regression method. The imputation regression model includes treatment group, all randomization strata as factors, and body weight at all previous visits (including baseline weight) as covariates. At least 100 imputations will be carried out. More imputations may be performed to improve the precision. The initial seed for both steps of the imputation will be 8704011.
2. Percent change from baseline in weight at Week 12 of each of these multiple imputed datasets will be analyzed by the ANCOVA model with treatment group, all randomization strata as factors, and the baseline weight as covariate.
3. Results from Step 2 will be combined using Rubin's method. Estimated treatment effect, standard error (SE), 95% CI, and p-value will be reported.

Descriptive statistics of body weight and percent change from baseline at each visit (including last assessment during treatment period) will be presented by treatment group based on observed and MI data.

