For all the other endpoints, presentation of analysis results will be limited to estimated treatment effect, 95% CI and/or descriptive statistics.

Absolute change in body weight, BMI, systolic and diastolic blood pressure and all body composition endpoints will be analyzed similarly by ANCOVA model and MI for missing data

as noted in [Section 3.8.2.1](#). The ANCOVA model will include treatment and all randomization strata as factors and baseline value as a covariate. The proportion of subjects with ≥ 5 cm increase of waist circumference will be analyzed by the logistic regression model and MI method in a similar fashion as the proportion of subjects with $\geq 10\%$ weight gain, using the same imputed dataset from the primary analysis of change from baseline in waist circumference in [Section 3.8.3.3](#).

The proportion of subjects in each BMI category will be analyzed based on each subject's by-visit assessment status using a logistic regression model including treatment group and randomization strata as factors, and baseline BMI as covariate. The model is based on the MI for missing postbaseline assessments. Rubin's rule is used to combine results from applying the logistic regression model on imputed datasets.

Proportion of subjects with shifts in BMI category by visit will also be analyzed based on each subject's by-visit assessment status using the logistic regression model mentioned above. Shifts are defined as follows:

- Proportion of subjects shifting from $\text{BMI} < 25 \text{ kg/m}^2$ at baseline to $\text{BMI} \geq 25 \text{ kg/m}^2$ by visit
- Proportion of subjects shifting from $\text{BMI} < 30 \text{ kg/m}^2$ at baseline to $\text{BMI} \geq 30 \text{ kg/m}^2$ by visit

The proportion of subjects in each blood pressure category will be analyzed based on the subject's by-visit assessment status using a logistic regression model including treatment group and randomization strata as factors, and baseline systolic and diastolic blood pressure as covariates. The model is based on the MI for missing postbaseline assessments. Rubin's rule is used to combine results from applying the logistic regression model on imputed datasets.

Number of responders and proportion for each blood pressure category are the mean number of responders and mean proportion from the imputed datasets, respectively.

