Proportion of subjects with shifts in blood pressure category by visit will also be analyzed based on each subject's by-visit assessment status using the logistic regression model described above. Shifts are defined as follows:

- Proportion of subjects shifting from Normal blood pressure at baseline to Stage 1 or Stage 2 Hypertension
- Proportion of subjects shifting from Normal or Elevated blood pressure at baseline to Stage 1 or Stage 2 Hypertension

The blood pressure categories will be defined as follows based on American Heart Association criteria:

- Normal: systolic and diastolic blood pressure of < 120 and $< 80 \text{ mmHg}$, respectively
- Elevated: systolic and diastolic blood pressure of ≥ 120 to ≤ 129 and $< 80 \text{ mmHg}$, respectively
- Stage 1: systolic blood pressure of ≥ 130 to $\leq 139 \text{ mmHg}$ or diastolic blood pressure of ≥ 80 to $\leq 89 \text{ mmHg}$

- Stage 2: systolic blood pressure of ≥ 140 mmHg or diastolic blood pressure of ≥ 90 mmHg.

The following laboratory parameters will be analyzed by MMRM model as described in [Section 3.8.3.4](#). The model will include treatment, visit, treatment-by-visit interaction, all randomization strata as categorical fixed effects; the baseline value will be included as the covariate. An unstructured variance-covariance matrix will be used.

- Percent and absolute change from baseline in fasting lipids (fasting triglycerides, LDL, HDL, total cholesterol), fasting glucose, HbA1c, fasting insulin, and HOMA-IR by visit
- Percent and absolute change from baseline in additional laboratory parameters including Apo B, Apo A1, Apo B/Apo A1, hs-CRP, IL-6 and TNFa by visit.

The proportion of subjects with metabolic syndrome at each visit will be analyzed by logistic regression model including treatment group and randomization strata as factors and baseline metabolic syndrome as covariate.

The proportion of subjects meeting each individual component criterion for metabolic syndrome (listed below) will be analyzed by visit using the same logistic regression model described above with the respective baseline value for each component as the covariate.

Additionally, a similar logistic regression model including treatment and randomization strata as factors will be used to analyze the proportion of subjects shifting from no metabolic syndrome at baseline to developing metabolic syndrome postbaseline. Data are based on observed values with no imputation for missing values.

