Metabolic syndrome is defined as meeting at least 3 of the following individual component criteria:

- Waist circumference, cm > 88 (women), > 102 (men)
- Triglycerides, mg/dL ≥ 150
- HDL cholesterol, mg/dL < 50 (women), < 40 (men)
- Glucose, fasting mg/dL ≥ 100
- Blood pressure, mm Hg $\geq 130/85$

The following endpoints will be analyzed by MMRM model as described in [Section 3.8.3.4](#), as applicable.

- Change from baseline in CGI-S score (between and within treatment groups) by visit
- Change from baseline in CGI-S score (between and within treatment groups) by visit and by diagnosis
- Change from baseline in IWQOL-Lite score by visit

IWQOL-Lite scale is a 31-item self-report measure of obesity-specific quality of life. The IWQOL-Lite provides an overall total score as well as scores on five domains: (1) physical function, (2) self-esteem, (3) sexual life, (4) public distress, and (5) work. The raw IWQOL scores will be transformed as follows ([Tessier et al, 2012](#)) before analyzed by the MMRM

method. The transformed scores range from 0 to 100, with 100 representing the best and 0 the most impaired quality of life.

$$\text{Transformed Score} = \frac{\text{maximum theoretical score} - \text{actual score}}{\text{test score range}} \times 100$$

CGI-I score and CGI-I responder status (≤ 2 versus > 2) at each visit will be summarized by treatment group. Descriptive statistics will be presented.

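### The model for new metabolic syndrome ignores how close each subject already is to the three-component threshold at baseline; adding the baseline component count would bring a small gain in efficiency

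*SAP*

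**What the plan says.** SAP 3.8.6 (Other Endpoints) analyses new metabolic syndrome as follows: "a similar logistic regression model including treatment and randomization strata as factors will be used to analyze the proportion of subjects shifting". The change of status that it counts is described as "from no metabolic syndrome at baseline to developing metabolic syndrome postbaseline". It uses observed values without imputation. The terms listed are treatment and the strata. SAP 3.8.2.1 gives the strata as diagnosis, "region [US vs non-US] and baseline BMI" (below 25, or 25 and above).

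The definition reads: "Metabolic syndrome is defined as meeting at least 3 of the following individual component criteria". Five components follow: waist circumference, triglycerides, HDL cholesterol, fasting glucose and blood pressure.

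Neighbouring models in SAP 3.8.6 carry a baseline term as well as the strata:

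- BMI category, with the same model used for BMI shifts: baseline BMI.
- Blood-pressure category, with the same model used for blood-pressure shifts: "randomization strata as factors, and baseline systolic and diastolic blood pressure as covariates".
- Metabolic syndrome by visit: "treatment group and randomization strata as factors and baseline metabolic syndrome as covariate".
- Each single component: the same model "with the respective baseline value for each component as the covariate".

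SAP 3.8.6 limits the other endpoints to an estimated effect, a 95% CI and/or descriptive statistics. SAP 3.8.4 does not include them in the hierarchy.

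**The concern.** The SAP does not spell out the denominator. The natural reading is subjects without the syndrome at baseline, who have 0, 1 or 2 components. A subject with two needs one more, and a subject with none needs three. Within a stratum the model treats them alike, although the count is likely to be a strong predictor of the outcome.

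The BMI shift is the closest parallel. Its subjects also start below the cutoff, and the SAP still adjusts for baseline BMI, which measures distance from that cutoff. The component count would do the same job here. The BMI stratum does so only in part, because it does not directly measure triglycerides, HDL, glucose or blood pressure.

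The count can vary at entry. Protocol 7.2.5 excludes fasting triglycerides above 500 mg/dL and fasting glucose of 126 mg/dL or more, while the component cutoffs are 150 and 100 mg/dL. The data are available: Protocol Table 3 schedules waist, vital signs and fasting biochemistry at Visit 2, before the first dose.

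At stake is some efficiency in one exploratory comparison of the arms.

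**Working it through.** **The plan's own power figure.** The only one is for the primary endpoint (SAP section 2): difference 8.5 − 5 = 3.5 points, SD 8, two-sided alpha 0.05, 200 per arm, 35% dropout. With 200 × (1 − 0.35) = 130 completers per arm, power is 94.1%; with 200 it is 99.2%. The stated level of at least 90% is reproduced. No power is stated for new metabolic syndrome.

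**Set-up.** Two logistic models were fitted to the same simulated trials:

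- Model A: treatment + diagnosis + region + BMI stratum.
- Model B: Model A + baseline component count (0, 1 or 2, linear).

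There were 12 scenarios with 1,500 trials each, and 130 or 200 subjects per arm, all taken as free of the syndrome at baseline and observed. The true odds ratio, conditional on the count, was 0.5 or 1.0. The count mix, the olanzapine risks by count, the share with BMI of 25 or more (25/45/65% by count) and the diagnosis and region shares are assumptions. Risk differences were standardised over the sample.

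**Results at odds ratio 0.5 (Model A → Model B).** Power here is the chance that the 95% CI excludes no effect.

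| Per arm | Counts 0/1/2 (%) | Risks (%) | Mean log OR | Mean SE | Power (%) | Risk-difference variance, B/A |
|---|---|---|---|---|---|---|
| 130 | 50/35/15 | 2/10/35 | −0.656 → −0.748 | 0.520 → 0.561 | 22.5 → 25.5 | 0.909 |
| 130 | 40/35/25 | 3/15/45 | −0.606 → −0.720 | 0.380 → 0.418 | 35.6 → 40.8 | 0.862 |
| 130 | 50/35/15 | 5/10/20 | −0.728 → −0.748 | 0.553 → 0.564 | 24.3 → 24.6 | 0.979 |
| 200 | 50/35/15 | 2/10/35 | −0.630 → −0.715 | 0.410 → 0.439 | 32.9 → 36.3 | 0.886 |
| 200 | 40/35/25 | 3/15/45 | −0.609 → −0.716 | 0.303 → 0.331 | 51.7 → 57.7 | 0.868 |
| 200 | 50/35/15 | 5/10/20 | −0.715 → −0.735 | 0.433 → 0.440 | 36.1 → 36.6 | 0.984 |

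The power gain runs from 24.6 − 24.3 = 0.3 to 57.7 − 51.7 = 6.0 points. Monte Carlo error on a single power is at most √(0.5 × 0.5/1500) = 1.3 points. Differences between the models are tighter because both use the same trials, but the smallest gains should be read as about zero.

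**At odds ratio 1.0.** Type I error is 4.1% to 5.0% for Model A and 3.8% to 5.5% for Model B. The risk-difference variance ratio is 0.830 to 0.984.

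**Over all 12 scenarios.** The mean ratio of standard errors (B/A) for the log odds ratio is 1.02 to 1.12, never below 1. Risk-difference variance falls by 2% to 17%.

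**Number of events.** Event rates were 6.9% to 17.7%, so 260 subjects give 0.069 × 260 ≈ 18 to 0.177 × 260 ≈ 46 events. In a sparser case (assumed counts of about 57/31/12% and risks of 2/8/30%), with about 14 events, power moved from 15.7% to 17.7%, and the standard error was 7% larger.

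**Size of a typical chance imbalance.** Take 130 per arm, counts of 40/35/25% and risks of 3/12/40%.

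- Average risk: 0.40 × 3 + 0.35 × 12 + 0.25 × 40 = 15.4%.
- One SD of the between-arm difference in two-component subjects: √(2 × 0.25 × 0.75/130) = 5.4 points.
- If these replace zero-component subjects, expected risk moves by 0.054 × (40 − 3) = 2.0 points.
- Risks of 17.4% against 15.4% with no drug effect give an odds ratio of (0.174/0.826)/(0.154/0.846) = 1.16. Adjustment for the BMI stratum would remove only part of this.

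**The case against.** The case for leaving the model alone has several sound parts.

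- **Precision.** A reader might infer that the unadjusted model gives a wider CI for the odds ratio than it need. On the log scale the reverse is true: adding a prognostic covariate to a logistic model increased the standard error in every scenario. The power gain arises because the estimate moves further from zero than the standard error grows, and the estimate then targets a different quantity, the odds ratio conditional on the count. This stands, and it is why a standardised risk difference belongs in the fix.
- **Bias.** A reader might infer that chance imbalance in near-threshold subjects biases the comparison. It does not: under randomisation it is part of the sampling error that a valid CI covers. Protocol 14.3 and SAP 3.4 also allow adjustment for important imbalances. That provision acts only after the data are seen, so it does not replace a prespecified term.
- **Oversight.** The by-visit model's covariate, baseline syndrome yes or no, is constant among subjects who start without the syndrome and could not be carried over. Leaving it out is therefore logical, and no SAP model uses a component count. But the omitted term was not replaced, whereas the BMI and blood-pressure shift models keep a continuous baseline measure.
- **Some baseline adjustment exists.** The BMI stratum is a baseline metabolic term, so the model is not without one.
- **Sparse data.** Subjects are under 40 with BMI below 30 at screening and no history of diabetes, so events may be few. With three main-effect strata the model already has five parameters, including the intercept.

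**Conclusion.** The point holds in a limited form. The model omits a baseline measure that is already collected and is probably prognostic, while the SAP's BMI-shift and blood-pressure-shift models include theirs. Under the assumed rates, adding the count brings about 0 to 6 points of power at an odds ratio of 0.5 and 2% to 17% less variance for a standardised risk difference, with type I error close to 5%. The standard error of the log odds ratio rises by 2% to 12%. All of these sizes depend on the assumed rates and could lie near the low end in this population.

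A reader might also infer that an important conclusion is at risk. The documents do not support that. Metabolic syndrome is not among the endpoints in Protocol 11.3, it appears in SAP 3.8.6 as an other endpoint, and no confirmatory test rests on it. The planned analysis is valid without the change, and the priority is low.

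**What to change.** In SAP 3.8.6, for the shift from no metabolic syndrome to metabolic syndrome:

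1. Add the number of components met at baseline (0, 1 or 2) as a single linear covariate beside treatment and the strata.
2. Report a risk difference standardised over the analysed subjects, with 95% CI, beside the odds ratio, and label the odds ratio as conditional on the count. SAP 3.8.3.1.1 already reports a risk difference for the weight-gain proportions.
3. State that the denominator is subjects without metabolic syndrome at baseline, and say how a missing baseline component is counted.

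No new data are needed. The cost is a short SAP clause, one more parameter (five to six with main-effect strata) where events may be few, and an odds ratio with a different meaning from the one now planned. As a non-confirmatory change, SAP section 5 asks only that it be listed and explained in the clinical study report.

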3.9. Safety Analysis

3.9.1. Adverse Events

AEs will be coded by System Organ Class and Preferred Term using the Medical Dictionary for Regulatory Activities (MedDRA®) Version 23.0 or higher. The verbatim term will be included in the AE listings.

An AE (classified by preferred term) will be considered as a treatment-emergent AE (TEAE) if the event is newly occurring or worsening on or after the date of first dose of study drug and within 7 days after the date of last dose of the study drug.

An overview table, including number and percentage of subjects with TEAEs, study-drug-related TEAEs, severe TEAEs, AEs leading to treatment discontinuation (AEDCs), serious AEs (SAEs), study drug-related SAEs, and deaths will be provided.

The number and percentage of subjects reporting TEAEs during the Double-blind Treatment Period will be presented by treatment group for the following categories:

- System organ class and preferred term
- Preferred terms in decreasing frequency, and also including the following subsets:
 - Experienced by $\geq 2\%$ of subjects in any treatment group
 - Experienced by $\geq 5\%$ of subjects in any treatment group and ≥ 2 times of olanzapine Group
- System organ class, preferred term, and severity
- System organ class, preferred term for severe TEAEs
- System organ class, preferred term, and relationship
- System organ class, preferred term for drug-related TEAEs
 - Experienced by $\geq 2\%$ of subjects in ALKS 3831 group by preferred term

If more than one AE is coded to the same preferred term for the same subject for the same period, the subject will be counted only once for that preferred term using the most severe and most related occurrence for the summarization by severity and by relationship to study drug.

In addition, the number and percentage of subjects reporting AEs and SAEs during the Safety Follow-up Period will be tabulated by the system organ class, preferred term, and treatment group.

For the subjects who prematurely discontinue the study drug and return for the bi-weekly visits, all AEs collected after discontinuation of the study drug will be summarized by system organ class, preferred term, and treatment group.

3.9.1.1. Deaths, Serious and Other Significant Adverse Events

The number and percentage of subjects who have SAEs and AEDCs will be summarized by preferred term and treatment group, and will be sorted by decreasing frequency for the ALKS 3831 group.

3.9.1.1.1. AEs of Special Interest

The incidence of a selected subset of relevant AEs in this class of drugs (eg, Movement Disorders (Including Extrapyramidal Syndrome [EPS] and Tardive Dyskinesia), and suicidal ideation and behavior) will be summarized by treatment group and preferred term. The selection of AEs per subset will be based on the preferred term, Standardized MedDRA queries (SMQs) or customized MedDRA queries (CMQs) in [Appendix 2](#) and [Appendix 3](#).

3.9.2. Clinical Laboratory Parameters

Laboratory parameters will be presented in conventional (ie, US) units. Unless specified otherwise, only scheduled laboratory parameters will be included in the summaries.

All laboratory data, including those collected at unscheduled visits, will be included in the listings.

Laboratory results (baseline and change from baseline) for the Safety Population during Double-blind Treatment Period for chemistry and hematology parameters will be summarized by treatment group and by visit.

The number (percentage) of subjects with potentially clinically significant (PCS) values at any postbaseline visit, will be summarized by treatment group. PCS criteria are presented in [Table 1](#). The denominator will be all subjects with non-PCS baseline and at least one postbaseline assessment in the Safety Population and the numerator will be the number of subjects with non-PCS baseline and PCS at postbaseline. All PCS values including baseline PCS values will be included in supportive listings.

For selected metabolic parameters (fasting total cholesterol, fasting HDL, fasting LDL, fasting triglycerides, fasting glucose, and HbA1c), an analysis of sustained PCS values will also be conducted. The percentage of subjects with sustained PCS values through the treatment period will be summarized. The denominator is all subjects with non-PCS at baseline and at least two postbaseline assessments, and the numerator is the number of subjects who met PCS criteria at the last 2 assessments within the treatment period.

Shift tables for metabolic parameters (fasting total, fasting HDL, fasting LDL cholesterol, fasting triglycerides, fasting glucose, and HbA1c) and liver function tests will be presented. The criteria are summarized in [Table 2](#), [Table 3](#), [Table 4](#) and [Table 5](#).

A listing of subjects who met Hy's Law will be provided. Subjects who met Hy's Law is defined as subjects who meet all of the following three criteria:

1. Alanine aminotransferase (ALT) or aspartate aminotransferase (AST) $\geq 3 \times$ upper limit of normal (ULN)
2. Total bilirubin $\geq 2 \times$ ULN
3. A non-elevated alkaline phosphatase (ALP) $< 2 \times$ ULN

Table 1: Criteria of Potentially Clinically Significant (PCS) Abnormality for Selected Analytes

Parameter	Criteria
Chemistry	
Albumin	<2.5 g/dL
Alkaline Phosphatase (U/L)	$\geq 3 \times \text{ULN}$
Alanine Aminotransferase (U/L)	$\geq 3 \times \text{ULN}$
Aspartate Aminotransferase (U/L)	$\geq 3 \times \text{ULN}$
Bilirubin, Total	$\geq 2.0 \text{ mg/dL}$
Blood Urea Nitrogen	$>30 \text{ mg/dL}$
Cholesterol, Random	$>300 \text{ mg/dL}$
Cholesterol, Fasting	$\geq 240 \text{ mg/dL}$
Cholesterol, HDL Fasting	$\leq 40 \text{ mg/dL}$
Cholesterol, HDL Fasting	Decrease $\geq 20 \text{ mg/dL}$
Cholesterol, LDL Fasting	$\geq 160 \text{ mg/dL}$
Cholesterol, LDL Fasting	Increase $\geq 30 \text{ mg/dL}$
Creatine Kinase (U/L)	$\geq 3 \times \text{ULN}$
Creatinine	$\geq 2.0 \text{ mg/dL}$
Glucose, Random	$<50 \text{ mg/dL}$ or $\geq 200 \text{ mg/dL}$
Glucose, Fasting	$<50 \text{ mg/dL}$ or $\geq 126 \text{ mg/dL}$
Glucose, Fasting	Increase $\geq 10 \text{ mg/dL}$
HbA1c	$\geq 5.7\%$
Potassium	$<3 \text{ mmol/L}$ or $>5.5 \text{ mmol/L}$
Lactate Dehydrogenase (U/L)	$>3 \times \text{ULN}$
Prolactin (Female)	$>30 \text{ ng/mL}$
Prolactin (Male)	$>20 \text{ ng/mL}$
Prolactin (Female)	$>3 \times \text{ULN}$
Prolactin (Male)	$>3 \times \text{ULN}$
Sodium	$<130 \text{ mmol/L}$ or $>150 \text{ mmol/L}$
Triglycerides, Fasting	$\geq 200 \text{ mg/dL}$
Triglycerides, Fasting	Increase $\geq 50 \text{ mg/dL}$

Table 1: Criteria of Potentially Clinically Significant (PCS) Abnormality for Selected Analytes (Continued)

Parameter	Criteria
Hematology	
Hematocrit (Female)	$\leq 32\%$
Hematocrit (Male)	$\leq 37\%$
Platelets	$< 75.0 \times 10^3 \text{ cells}/\mu\text{L}$ or $\geq 700.0 \times 10^3 \text{ cells}/\mu\text{L}$
Leukocytes	$\leq 2.8 \times 10^3/\mu\text{L}$ or $\geq 16.0 \times 10^3/\mu\text{L}$
Neutrophils, Absolute	$< 1.5 \times 10^3/\mu\text{L}$ $< 1.0 \times 10^3/\mu\text{L}$

Abbreviations: HDL= high-density lipoprotein; LDL=low-density lipoprotein; ULN=upper limit of normal.

Table 2: Shifts Category from Baseline to Any Postbaseline for Selected Lipid Parameters

Parameter	Shift Criterion
Total cholesterol (fasting) mg/dL	Normal (< 200) to borderline (≥ 200 and < 240)
	Borderline (≥ 200 and < 240) to high (≥ 240)
	Normal (< 200) to high (≥ 240)
LDL cholesterol (fasting) mg/dL	Normal (< 100) to borderline (≥ 100 and < 160)
	Borderline (≥ 100 and < 160) to high (≥ 160)
	Normal (< 100) to high (≥ 160)
HDL cholesterol (fasting) mg/dL	Normal (≥ 40) to low (< 40)
Triglycerides (fasting) mg/dL	Normal (< 150) to borderline (≥ 150 and < 200)
	Borderline (≥ 150 and < 200) to high (≥ 200)
	Normal (< 150) to high (≥ 200)

Abbreviations: HDL=high-density lipoproteins; LDL=low-density lipoproteins.

Table 3: Shift Category from Baseline to Any Postbaseline in Glucose and HbA1c

Parameter	Shift Criterion
Glucose (fasting) mg/dL	Normal (< 100) to impaired (≥ 100 and < 126)
	Impaired (≥ 100 and < 126) to high (≥ 126)
	Normal (< 100) to high (≥ 126)
HbA1c % ^a	Normal ($< 5.7\%$) to borderline ($\geq 5.7\%$ and $< 6.5\%$)
	Borderline ($\geq 5.7\%$ and $< 6.5\%$) to high ($\geq 6.5\%$)
	Normal ($< 5.7\%$) to high ($\geq 6.5\%$)

^a Subjects with HbA1c $\geq 6.0\%$ were excluded from enrolling in the studies.

Table 4: Shift Category from Baseline to Any Postbaseline in Liver Function Test

Parameter	Criterion
Alanine Aminotransferase (ALT) (U/L)	Shift from Normal to $\geq 3 \times$ ULN
	Shift from Normal to $\geq 5 \times$ ULN
	Shift from Normal to $\geq 10 \times$ ULN
Aspartate Aminotransferase (AST) (U/L)	Shift from Normal to $\geq 3 \times$ ULN
	Shift from Normal to $\geq 5 \times$ ULN
	Shift from Normal to $\geq 10 \times$ ULN
Bilirubin, Total (mg/dL)	Shift from Normal to $> 1 \times$ ULN
	Shift from Normal to $\geq 2 \times$ ULN

Abbreviations: ULN=upper limit of normal.

Table 5: Prolactin – Shift Categories from Baseline to Any Postbaseline

Prolactin (ng/mL)
Shift from (Low or Normal) to ($\geq 3 \times$ ULN)
Shift from ($\geq 3 \times$ ULN) to (Low or Normal)

Abbreviations: ULN=upper limit of normal.

